#### **Exclusion criteria:**

- Received CAB+RPV LA or oral ART regimen as part of a clinical trial
- Treatment naïve

#### Index date

Date of first regimen of interest

#### **Censoring criteria:**

- Discontinuation of regimen of interest
- Death
- Loss to follow-up (12 months after last clinical contact)
- Study end (end of observation period: 29FEB2024, 28FEB2025, 28FEB2026)

#### 6.3. \*Variables

#### 6.3.1. Exposure definitions

Exposure is defined as receiving CAB+RPV LA injectable regimen or an oral ART regimen.

#### 6.3.2. Outcome definitions

#### 6.3.2.1. Baseline characteristics

- Demographic characteristics at index
  - o Age (years, as well as categorized as 18-50, 50-64, 65+)
  - o Sex (male, female)
  - o Race (African American/Black, Asian, White, other race, unknown)
  - o Ethnicity (Hispanic, non-Hispanic)
  - Marital status (Single, married/domestic partner, widowed, separated/divorced, unknown)
  - Geographic region (Northeast, Midwest, South, West, US Territories)
  - o Risk of HIV transmission (MSM, PWID, Heterosexual, Vertical, Other)
  - Payer type (Medicaid, Medicare, Commercial insurance, AIDS Drug Assistance Programs (ADAP)/Ryan White, Cash)
- Clinical characteristics at index
  - Years since HIV diagnosis
  - Years since ART initiation
  - o AIDS diagnosis at baseline
  - Years since first OPERA visit
  - Veterans Aging Cohort Study (VACS) Mortality Index score
  - $\circ$  Pregnancy (ever Y/N, and currently Y/N)
  - Weight (kg)

- $\circ$  BMI (kg/m^2)
  - $< 30 \text{ kg/m}^2$
  - $\bullet$  30-<40 kg/m^2
  - $\ge 40 \text{ kg/m}^2$
- Co-infections
  - Hepatitis B co-infection
  - Hepatitis C co-infection
  - Syphilis infection (ever)
- o Comorbidities
  - Autoimmune disease
  - Cardiovascular disease
  - Invasive cancer
  - Endocrine disorder
  - Mental health disorder
  - Liver disease
  - Bone disorder
  - Peripheral neuropathy
  - Renal disease
  - Hypertension
  - Substance abuse
  - Any of the above
- Concomitant Medications
  - Anticonvulsants
    - Carbamazepine
    - Oxcarbazepine
    - Phenobarbital
    - Phenytoin
  - Antimycobacterials
    - Rifampin
    - Rifapentine
    - Rifabutin
  - Glucocorticoids
    - Dexamethasone
  - Macrolide or ketolide antibiotics
    - Azithromycin
    - Clarithromycin
    - Erythromycin
  - Narcotic analgesic
    - Methadone
- ART regimens prior to CAB+RPV LA
  - Number of core agents experienced
  - o Number of ARV classes experienced
  - Duration of last ARV regimen
  - o Prior core agent class
- Baseline virologic characteristics
  - o HIV viral load
    - Test result available (yes/no)
    - Continuous (copies/mL and log10 copies/mL)

- Categorical
  - o <50 copies/mL
  - $\circ$   $\geq$ 50 to  $\leq$ 200 copies/mL
  - $\circ \geq 200 \text{ to } < 1,000 \text{ copies/mL}$
  - $\circ \ge 1,000 \text{ to } < 10,000 \text{ copies/mL}$
  - $\circ$  >10,000 to <100,000 copies/mL
  - $0 \ge 100,000 \text{ copies/mL}$
  - Missing
- Baseline immunologic characteristics
  - o CD4 cell count
    - Test result available (yes/no)
    - Continuous (cells/μL)
    - Categorical
      - $\circ$  >500 cells/ $\mu$ L
      - >350 to  $\leq 500$  cells/ $\mu$ L
      - $\circ$  >200 to  $\leq$ 350 cells/ $\mu$ L
      - $\circ$  >50 to  $\leq$ 200 cells/ $\mu$ L)
      - $\circ \leq 50 \text{ cells/}\mu L$
      - o Missing

#### 6.3.2.2. Patterns of use

Patterns of use will be described in terms of the CAB+RPV LA dosing schedule at initiation and last follow-up. Initiation doses (first 2 doses) will be categorized as monthly (600/900 mg at 1st injection followed by 400/600 mg as of the 2nd injection) or every other month (600/900 mg at all injections). Dosing at last follow-up will be categorized as monthly (400/600 mg) or every other month (600/900 mg).

#### 6.3.2.3. Persistence

Persistence will be measured as time on CAB+RPV LA regimen (months, continuous) as well as the number and proportion of PWH receiving CAB+RPV LA regimen at study end.

Among PWH still receiving CAB+RPV LA regimen at study end, time on CAB+RPV LA will be reported (months, continuous).

Among PWH who discontinued CAB+RPV LA regimen at any point during follow-up, time receiving CAB+RPV regimen prior to discontinuation (months, continuous) will be reported. Among discontinuers with ≥1 VL available during follow-up, viral load at discontinuation will be assessed (VL <200 copies/mL vs. ≥200 copies/mL).

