## **Study Period:**

- o Year 3:
  - Period of eligibility: 21JAN2021-31DEC2023
  - Period of observation: 21JAN2021-29FEB2024
- O Year 4:
  - Period of eligibility: 21JAN2021-31DEC2024
  - Period of observation: 21JAN2021-28FEB2025
- o Year 5:
  - Period of eligibility: 21JAN2021-31DEC2025
  - Period of observation: 21JAN2021-28FEB2026

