#### 6.3.2.4. Discontinuation

Discontinuation will be defined as >67 days after last injection (monthly dosing) or >127 days after last injection (every other month dosing).

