# 6.7. \*Data analysis

# 6.7.1. Primary Analysis

## 6.7.1.1. Main Analytical approach

Baseline characteristics and outcomes will be described using counts and absolute and relative frequencies for categorical variables and medians with interquartile ranges (IQR) for continuous variables. For outcomes assessed at any point during follow-up, incidence rates will be estimated using unadjusted Poisson regression, accounting for person-time since index (i.e., first CAB+RPV LA injection).

Analyses will be stratified by viral load (<50 copies/mL vs. ≥50 copies/mL), BMI (<30 kg/m² vs. ≥30 kg/m²), age (18-50, 50-64, ≥65 years), race/ethnicity (non-Hispanic Black, Hispanic, non-Hispanic White), and sex/race (non-Hispanic Black men, Hispanic men, Black women) strata at first CAB+RPV LA injections as sample size allows to assess characteristics, adherence, persistence, discontinuation and virologic effectiveness. Other demographic and clinical variables may also be considered for stratification, if relevant.

Factors including age, sex, race, geographic region, BMI, IDU, CD4 count, any comorbidities associated with confirmed virologic failure will be assessed using multiple logistic regression.

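### Persistence is summarised by unadjusted medians and a proportion at the data cut, so the result moves with length of follow-up even when persistence does not change

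*Protocol*

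**What the plan says.** Primary objective 2 (Protocol section 5) covers persistence, adherence and discontinuation at Years 3, 4 and 5 of availability.

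Section 6.3.2.3 fixes the persistence measures:
- For the whole cohort: "Persistence will be measured as time on CAB+RPV LA regimen (months, continuous) as well as the number and proportion of PWH" on the regimen at study end.
- For those still treated: "Among PWH still receiving CAB+RPV LA regimen at study end, time on CAB+RPV LA will be reported (months, continuous").
- For those who stopped: "time receiving CAB+RPV regimen prior to discontinuation (months, continuous) will be reported".

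Section 6.7.1.1 summarises continuous variables by "medians with interquartile ranges (IQR) for continuous variables". For outcomes assessed at any point in follow-up it adds that "incidence rates will be estimated using unadjusted Poisson regression, accounting for person-time since index".

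Under Study Period in section 6.2, the Year 3 analysis has "Period of eligibility: 21JAN2021-31DEC2023" with observation to 29FEB2024. Year 5 has "Period of eligibility: 21JAN2021-31DEC2025" with observation to 28FEB2026. Year 4 follows the same pattern, with entry to 31DEC2024 and observation to 28FEB2025. Study end is listed among the censoring criteria.

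Section 6.3.2.4 defines discontinuation as more than 67 days after the last injection for monthly dosing, or ">127 days after last injection (every other month dosing").

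**The concern.** For anyone still treated at the cut, time on regimen is only the time from first injection to the cut. The protocol recognises this as censoring, but the stated summaries treat each duration as complete. With entry staggered over three to five years, three things follow.

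- The all-patient median reflects both how long people stay on treatment and how long ago they started.
- The proportion on regimen at study end falls as average follow-up lengthens.
- The discontinuer-only median is short, because only people who stopped before the cut contribute to it.

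A reader who sets Years 3, 4 and 5 side by side would see a falling proportion, suggesting worse persistence, and rising medians, suggesting better persistence. Both could arise with no change at all. The same distortion applies between subgroups, or against the oral ART cohort, where uptake over calendar time differs.

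**Working it through.** The protocol gives no persistence figure to reproduce. The check asks what its summaries would show if true persistence were identical at every cut.

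**Inputs from section 6.2.** A is days from first to last entry, O is days from first entry to the cut, and m = O − A is the shortest possible follow-up.

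| Cut | A | O | m | Longest follow-up |
|---|---|---|---|---|
| Year 3 | 1,074 | 1,134 | 60 | 37.3 months |
| Year 4 | 1,440 | 1,499 | 59 | 49.2 months |
| Year 5 | 1,805 | 1,864 | 59 | 61.2 months |

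**Assumptions, none in the protocol.** Constant discontinuation hazard λ = 0.15 per year; uniform entry; no death or loss; discontinuation recorded when it happens.

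**Truth at every cut.** 12-month persistence = exp(−0.15) = 86%. Median = ln 2 / 0.15 = 4.62 years = 55 months.

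**Proportion on regimen at study end** = [exp(−λm) − exp(−λO)] / (λA), with days divided by 365.25:
- Year 3: (0.9757 − 0.6277) / 0.4411 = 79%
- Year 4: (0.9761 − 0.5403) / 0.5914 = 74%
- Year 5: (0.9761 − 0.4651) / 0.7413 = 69%

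**Median time on regimen, everyone.** Solve exp(−λx)·(O − x)/A = 0.5 for x. This gives 15.8, 19.2 and 22.1 months.

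**Median among discontinuers.** This is the median of the density proportional to λ·exp(−λx)·P(follow-up > x). It gives 9.8, 12.5 and 15.0 months.

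**Poisson rate, if applied to discontinuation.** 15 per 100 person-years at all three cuts.

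**Sensitivity to the hazard.** At Year 5 with uniform entry, the proportion on regimen is 78% at 10% per year and 50% at 30% per year. The fall from Year 3 to Year 5 also appears when 12-month persistence is assumed to be 95% (92.0, 89.8, 87.6) or 70% (58.4, 50.7, 44.4).

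**Sensitivity to the entry pattern.** Hold 12-month persistence at 80% and look at Year 5. Entry rising over time gives 68.9% on regimen and a median of 13.7 months. Front-loaded entry gives 47.9% and 26.8 months. True persistence is the same in both.

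**Discontinuation windows against the cut.** The shortest follow-up, 59-60 days, is below both windows. Counting back from 28FEB2026, day 128 falls on that date for an injection on 23OCT2025, and day 68 for one on 22DEC2025. Anyone first injected after those dates (every-other-month and monthly dosing respectively) cannot meet the definition by the Year 5 cut. For the longer window that is 24OCT2025 to 31DEC2025, or 69 of 1,806 entry days (both ends counted) = 3.8% of starters under uniform entry.

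**The case against.** The strongest reply is the Poisson rule. Section 6.7.1.1 applies it to outcomes at any point in follow-up, and section 6.3.2.3 uses the same idea for discontinuers. Discontinuation is the complement of persistence, and under a constant hazard its rate does not drift. A reader might infer that nothing reported under primary objective 2 can be compared across years or subgroups. The protocol does not support that, because the distortion lies in the persistence summaries. What remains is that the rate is not named as the persistence measure, is exactly stable only under a constant hazard, and gives no persistence at a fixed time.

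A second reply is that the estimator belongs in the SAP, which is not at hand and may add Kaplan-Meier. That is fair, and the absence of a named method is not the point. The point is what section 6.3.2.3 does fix as the measure of a primary-objective outcome.

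Third, the three cuts are cumulative descriptive updates, and no objective sets out to compare the years. The proportion on regimen is a true description of use at the cut. That stands, and it is a reason to keep the figure under that label. However, subgroup comparisons are planned (section 6.3.3.2), and so is a comparison with oral ART (secondary objective 3).

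Two further inferences are tempting but go too far. The all-patient median does not simply measure calendar entry. At Year 5 under uniform entry the median time since first injection is 31.6 months, while the median time on regimen is 24.8, 22.1 or 16.5 months at hazards of 10, 15 or 30% per year, so it reflects both. Nor does the defect carry over to confirmed virologic failure. Section 6.3.2.6 sets those proportions at fixed months from initiation and states no denominators, and the Poisson rule covers that outcome too.

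**Conclusion.** The concern holds for the persistence summaries in section 6.3.2.3. They mix persistence with length of follow-up and shift between cuts, and between groups with different uptake, when persistence is unchanged. In the illustration the proportion on regimen drops by 10 percentage points from Year 3 to Year 5 (79% to 69%), while the all-patient median rises by about 6 months (16 to 22) and stays far below the true 55. The direction was the same in every scenario tried. The size depends on the assumed hazard and entry pattern, neither of which the protocol gives.

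The late starters who cannot yet be classed as discontinued are a minor addition, about 3.8% at Year 5 for the longer window. Someone inside the window has by definition not yet discontinued, and the 79%, 74% and 69% arise without this effect.

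The change should be made because the outcome belongs to a primary objective and the better summary is nearly free. It is not a flaw that invalidates the study.

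**What to change.** Amend section 6.3.2.3, with a matching line in section 6.7.1.1:
- Make Kaplan-Meier time to discontinuation the persistence analysis, with 95% CI and numbers at risk.
- Report persistence at 6, 12, 24, 36 and 48 months as far as each cut's follow-up allows (48 months is out of reach at Year 3, where the longest follow-up is 37.3 months), and the median if reached.
- Apply the discontinuation definition in section 6.3.2.4 and the censoring criteria in section 6.2 as they stand. Discontinuation becomes the event; death, loss to follow-up and study end censor.
- Keep the number and proportion on regimen at study end as a description of current use only.
- If time to discontinuation among discontinuers is still shown, do not present it as an estimate of persistence.
- State whether the Poisson rate will be applied to discontinuation; it is a useful companion figure.

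The cost is a wording change and standard output from data already extracted. No new variables are needed.

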#### 6.3.2.4. Discontinuation

Discontinuation will be defined as >67 days after last injection (monthly dosing) or >127 days after last injection (every other month dosing).

#### 6.3.2.5. Adherence

Adherence will be assessed by estimating the number of individuals that missed one or more consecutive injections without taking daily oral bridging therapy or any other oral ARV regimen while not on CAB+RPV LA regimen and mean and median number of injections missed. The number of individuals who received the injections seven or more days later than their scheduled injection visit and median duration of delayed injections in persons using bridging therapy will be evaluated.

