#### Proposed changes in study objectives:

The proposed changes to the study objectives are:

- 1. Primary objective:
  - a. Factors associated with confirmed virologic failure was not listed as a separate primary objective in the initial study but was assessed as part of virologic effectiveness analysis. It is called out as a separate primary objective in this study as we will enough numbers to conduct this analysis.
- 2. Secondary objective:
  - a. Sub-group analyses by viral load (<50 copies/mL, 50 <200 copies/mL, and ≥200 copies/mL), BMI (<30 and ≥30 kg/m²) and age (<18, 18-50, 50-64, ≥65 years) at initiation to assess characteristics, adherence, persistence, discontinuation and virologic effectiveness are explicitly called out as a secondary objective in this study. Some of the sub-groups listed were evaluated in the initial study but was not listed as a study objective.
- 3. Oral lead-in and oral bridging explored in the initial study will not be assessed in this study as these events cannot be reliably observed in the OPERA data.

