#### **Primary Objectives:**

- 1. To describe baseline demographics, clinical characteristics and patterns of use among PWH receiving CAB+RPV LA at Year 3, Year 4, and Year 5 of availability
- 2. To assess the persistence, adherence and discontinuation among PWH receiving CAB+RPV LA at Year 3, Year 4, and Year 5 of availability
- 3. To assess virologic effectiveness among PWH receiving CAB+RPV LA at Year 3, Year 4, and Year 5 of availability
- 4. To assess factors associated with confirmed virologic failure among PWH receiving CAB+RPV LA regimen at Year 3, Year 4, and Year 5 of availability

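### Two of the four adherence measures rest on oral bridging, which the protocol says OPERA cannot reliably observe, and delay duration is specified only for people who bridged

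*Protocol*

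**What the plan says.** Primary objective 2 (Protocol section 5) is "To assess the persistence, adherence and discontinuation among PWH receiving CAB+RPV LA". Section 6.3.2.5 is the only definition of adherence. It lists four measures:

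1. the number of people who "missed one or more consecutive injections without taking daily oral bridging therapy or any other oral ARV regimen while not on CAB+RPV LA regimen";
2. the "mean and median number of injections missed";
3. the number of people whose injections came "seven or more days later than their scheduled injection visit";
4. the "median duration of delayed injections in persons using bridging therapy".

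In the Summary of Changes for Amendment 1, under the proposed changes in study objectives, the protocol says that oral lead-in and oral bridging "will not be assessed in this study as these events cannot be reliably observed in the OPERA data". The decision, without the reason, is repeated in the Revision Chronology and in the amendments table of section 2. None of the changes listed for Amendments 2 and 3 restores bridging. Section 6.7.1.2 plans no sensitivity analyses, and the limitations in section 6.9 do not mention bridging.

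**The concern.** Measures 1 and 4 can be computed only if the analyst knows who bridged. The protocol states, as a property of its data source, that this is not reliably known. A person whose gap was bridged but whose bridging was not recorded looks like a person with an uncovered miss, so measure 1 is pushed upward.

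Measure 4 has a second weakness that does not depend on data quality. As worded, it summarises delay only among people using bridging. No duration is specified for a late injection without bridging, although there a delay is time without cover. Section 4 justifies the attention to dosing visits by the risk of rebound and resistance when doses are missed, so the summary leaves out the people to whom that rationale applies most directly.

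At stake are two reported components of a primary outcome. The conflict is fixed in the protocol itself, so an analysis plan that follows section 6.3.2.5 would inherit it.

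**Working it through.** **Step 1: which measures need bridging status?**

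| Measure in 6.3.2.5 | Needs bridging status? |
|---|---|
| People with missed, uncovered injections | Yes: covered misses are excluded |
| Mean and median number missed | Not stated |
| People seven or more days late | No, on the natural reading; the closing phrase about bridging users could be read as governing this part too |
| Median delay duration | Yes: restricted to bridging users |

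The dependence is certain for two of the four.

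**Step 2: is the statement about bridging still in force?** It gives a reason about OPERA, and OPERA is still the data source (section 6.4). When Amendment 2 moved the age limit that Amendment 1 had set, the change was logged; nothing comparable is logged for bridging. The current objectives, patterns of use (6.3.2.2) and discontinuation (6.3.2.4) contain no bridging element. Section 6.3.2.5 is the exception and looks like wording left over from before Amendment 1.

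**Step 3: direction and possible size for measure 1.** Let

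- p = proportion of the cohort who truly missed without bridging,
- b = proportion who missed but bridged,
- s = share of that bridging that is recorded.

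Then observed proportion = p + b(1 − s), and bias = b(1 − s). This is never negative, and it is zero when s = 1. It treats unreliable observation as under-recording. A bridging record for tablets that were not taken would act the other way, and the protocol does not discuss that case.

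The protocol gives none of p, b or s, so the values below are assumptions. For scale, the protocol's own precision at n = 1843 and a proportion of 0.10 is reproduced first: width = 2 × 1.96 × √(0.10 × 0.90 / 1843) = 0.0274, printed as 0.03 in Table 1. The half-width is 1.37 percentage points.

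With p = 10% and b = 5% (assumed):

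| s | Observed | Bias (points) | Bias / half-width |
|---|---|---|---|
| 0% | 15.0% | 5.0 | 3.65 |
| 50% | 12.5% | 2.5 | 1.83 |
| 75% | 11.25% | 1.25 | 0.91 |
| 100% | 10.0% | 0 | 0 |

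Over p = 5–15%, b = 2–10% and s = 0–75%, the bias runs from 2% × 0.25 = 0.5 points to 10% × 1 = 10 points, or about 0.3 to 10 half-widths. The range shows only that the bias could be negligible or could dominate sampling error. It is not an estimate. The larger cohorts expected in later years would narrow the interval but leave the bias unchanged.

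**Step 4: measure 4.** No arithmetic is needed. The summary describes only people recorded as bridging. How small a part of all late injections that is cannot be derived from the protocol.

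**The case against.** The strongest reply is that the statement about observability stands only in a change summary, and a difference between an amendment log and current text is not an error in itself. That rule covers superseded wording. Here the log gives a factual reason for a decision that remains in force, so the reply does not dispose of the point. A narrower form has some weight: dropping bridging as a topic of study is not the same as using recorded oral ART to qualify a missed injection. The clash is therefore plainest for delay duration, which is summarised expressly in bridging users.

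Other parts of the reply stand:

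- The condition in measure 1 also covers other oral regimens. Section 6.4 reports 4.5 million ART prescriptions in the records, so a switch to a prescribed oral regimen may be visible. The stated gap in the data concerns oral lead-in and bridging.
- Counting only uncovered misses is a legitimate concept of adherence. The difficulty is that these data cannot support it reliably.
- How bridging is ascertained could be left to an analysis plan that is not shown. That would not change the restriction to bridging users, which the protocol fixes.

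A reader might infer that late injections in general are mismeasured. The documents do not support that, because the seven-day count needs only the injection and scheduled dates on the natural reading. A reader might also infer that subgroup contrasts are biased. If the share of people with a miss who bridged and the share of bridging recorded are the same in every stratum, each stratum's count is multiplied by the same factor and ratios between strata are unchanged. Nothing in the protocol indicates that either share differs between strata.

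**Conclusion.** The point holds for two measures. The count of people with uncovered misses is biased upward to the extent that bridging goes unrecorded, and the median delay omits late injections without bridging. The first conclusion rests on the protocol's own statement about OPERA and on reading it as under-recording. The second follows from the wording of section 6.3.2.5 alone.

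The size is unknown from the documents. Any inflation factor for the missed-injection count would only reflect assumed rates of bridging and recording. It would also go too far to call the whole adherence outcome compromised: the seven-day count is not shown to be wrong, and the number of injections missed is not clearly conditioned on bridging. The change is worth making because the outcome is primary, the protocol contradicts itself, and the repair is small.

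**What to change.** Reconcile section 6.3.2.5 with the Amendment 1 decision:

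- Report missed injections (people with at least one, and mean and median number) from injection dates in all CAB+RPV LA users, and say that the count does not depend on oral cover.
- Report median (IQR) days late among all users with a late injection, and keep the seven-day count as a date-based measure.
- Keep the count of misses without recorded oral ART as a secondary descriptive item only.
- State in section 6.9 that bridging is under-captured and that this item therefore tends to overstate uncovered misses.

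The cost is a few sentences. No new data are needed: discontinuation in 6.3.2.4 already uses injection dates, and the seven-day count already needs the scheduled date. Year 5 preliminary tables are planned for July 2026 in section 3. The drawback is that some gaps that were truly bridged will count as missed or late in the date-based measures. The protocol should say so openly.

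### No adherence measure in 6.3.2.5 is divided by injections due, so the person counts and the mean number missed mix adherence with length of follow-up and dosing schedule

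*Protocol*

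**What the plan says.** Protocol section 6.3.2.5 gives four kinds of summary:

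- People who missed injections: "Adherence will be assessed by estimating the number of individuals that missed one or more consecutive injections without taking daily oral bridging therapy" or another oral regimen.
- The "mean and median number of injections missed".
- People with late injections: "The number of individuals who received the injections seven or more days later than their scheduled injection visit".
- The "median duration of delayed injections in persons using bridging therapy".

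The section mentions neither the number of injections due nor a time window. The next section, 6.3.2.6, does anchor the virologic outcomes, at 6, 12, 24, 36, 48 and 60 months.

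Three other parts of the protocol bear on this:

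- **Follow-up.** The Year 5 cut has "Period of eligibility: 21JAN2021-31DEC2025" and "Period of observation: 21JAN2021-28FEB2026". The Year 3 cut has "Period of observation: 21JAN2021-29FEB2024".
- **Schedule.** Section 6.3.2.2 recognises monthly and every-other-month dosing.
- **Use.** Adherence belongs to primary objective 2 at Years 3, 4 and 5. Section 6.3.3.2 says it will be compared across strata of viral load, BMI, age, race/ethnicity and sex/race.

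Section 6.7.1.1 adds that outcomes assessed at any point in follow-up will have Poisson incidence rates using person-time since index. It does not name adherence.

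**The concern.** An injection can be late or missed only when one is due. A person with 30 injections due has ten times as many occasions to be counted as a person with 3. The number ever late, the number ever missed and the mean number missed therefore depend on two things besides adherence: how long the person was followed, and how often injections were scheduled.

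Both vary in this study. Follow-up lengthens from one annual cut to the next, and strata may differ in persistence or in the share on monthly dosing. A reader of the Year 3, 4 and 5 tables, or of a comparison between strata, could take a difference in opportunity for a difference in adherence. Adherence is part of a primary objective and the protocol intends comparisons with it, so the choice of measure matters.

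**Working it through.** The protocol states no adherence figure, so there is none to reproduce. The check asks what the stated measures would show if adherence per injection never changed.

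**Inputs from the protocol (Study Period; 6.3.2.2)**
- Year 5 cut: potential follow-up runs from about 1.9 months (index 31 December 2025, end 28 February 2026) to 61.2 months (index 21 January 2021). The maximum is 37.3 months in the Year 3 cut and 49.2 in the Year 4 cut.
- Injections due, n: about one per month, or one per two months.

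**Assumed input**
- p, the chance that a due injection is late or missed: 5%, with a range of 2% to 10%. It is taken as constant, equal for everyone and independent between injections. None of this is in the documents.

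**Formulas.** Share with at least one event = 1 − (1 − p)^n. Mean number of events = n × p.

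At p = 0.05:

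| Follow-up | Monthly: n, share, mean | Every other month: n, share, mean |
|---|---|---|
| 12 months | 12, 46.0%, 0.60 | 6, 26.5%, 0.30 |
| 24 months | 24, 70.8%, 1.2 | 12, 46.0%, 0.60 |
| 36 months | 36, 84.2%, 1.8 | 18, 60.3%, 0.90 |
| 60 months | 60, 95.4%, 3.0 | 30, 78.5%, 1.5 |

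(The 26.5% is 1 − 0.95^6 = 0.2649, so 26% to the nearest whole number.)

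At 60 months the shares are 70.2% and 45.5% for p = 0.02, and 99.8% and 95.8% for p = 0.10.

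**By data cut**, at p = 0.05, with index dates spread evenly over the eligibility window and administrative censoring only (both assumed):

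| Cut | Monthly | Every other month |
|---|---|---|
| Year 3 | 57.2% | 35.9% |
| Year 4 | 65.1% | 43.5% |
| Year 5 | 70.9% | 49.8% |

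**If the Poisson rate of 6.7.1.1 were applied**, at p = 0.05:
- Person-time stopped at the first event: the rate is p divided by the interval in years. Monthly: 0.05 ÷ (1/12) = 0.60 per person-year. Every other month: 0.05 ÷ (2/12) = 0.30. Both are flat over follow-up, but they differ twofold.
- Full person-time since index, people with an event in the numerator: monthly falls from 0.460 ÷ 1 = 0.46 at 12 months to 0.954 ÷ 5 = 0.19 at 60 months. Every other month falls from 0.26 to 0.785 ÷ 5 = 0.16.

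**Clustering.** If p differs between persons, the share ever affected is lower at the same mean p. For example, if p follows a Beta(0.5, 4.5) distribution (mean 10%, spread assumed), the shares after 3, 6, 12, 24 and 30 due injections are 23%, 36%, 49%, 61% and 65%. With a constant 10% they are 27%, 47%, 72%, 92% and 96%. The rise is weaker but remains.

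**With injections due as denominator**, the expected result equals p at every follow-up length, on both schedules and at every cut.

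**The case against.** The strongest reply rests on 6.7.1.1. Ever missing an injection, or ever being late, is naturally an outcome assessed at any point in follow-up, so the person-time rate may be meant to apply. If it is, the rise with follow-up disappears or reverses, as shown above. This stands as a limit on the point. A reader might infer that reported adherence must appear to worsen every year and that the bias runs against people who stay longest on the regimen. The documents do not support that without qualification: it holds for the raw counts and the mean, and only if they are not replaced by rates. Section 6.3.2.5 does not say which applies, the mean and median number missed are not written as rates, and no version of the rate corrects for schedule.

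Four further points can be made:

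- **Schedule is not a planned stratum, and the share on each schedule is not given.** This is correct. A distortion between strata needs the monthly share or the follow-up to differ between them, so its size cannot be stated. Sections 6.3.2.2 and 6.3.2.3 do describe schedule and time on regimen, but separately, which does not adjust the adherence figures.
- **Not every measure accumulates.** This is correct. The median number missed may stay at zero, and the median delay among bridging users does not build up with follow-up.
- **The discontinuation rule in 6.3.2.4 ends follow-up after long gaps.** It limits long runs of misses. Single misses and short delays can still accumulate.
- **The study is descriptive, and denominators are often left to a SAP.** A count of people who ever missed an injection is a legitimate description. But the protocol itself chose these measures and plans to compare them across strata, so this is a stated choice and not an omitted detail.

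**Conclusion.** The point holds in a limited form. No measure in 6.3.2.5 uses injections due or a fixed window. As written, the number of people ever missed, the number ever late by seven or more days and the mean number missed depend on follow-up and on schedule, even at equal per-injection adherence.

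The 12- and 60-month shares in the brief illustrate the size at an assumed 5% per due injection. For a given mean chance they are upper bounds, because they assume that it is the same for everyone and independent between injections.

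The schedule effect survives every reading of 6.7.1.1. The follow-up effect does not, and it rests on whether that section covers adherence, which the protocol leaves open. The defensible conclusion is that differences between the Year 3, 4 and 5 cuts and between strata could partly reflect opportunity. It is not established that they will, or in which direction any stratum would be shifted. The change is worth making because the measure serves a primary objective and the better one is cheap.

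**What to change.** In section 6.3.2.5, make the main adherence measures the proportions of injections given on time, given seven or more days late, and missed. Divide each by all injections due between index and end of follow-up. Report them overall and by dosing schedule, with standard errors that allow for repeated injections in the same person. Keep the person-level counts as descriptive rows beside the median number of injections due. State whether the Poisson rate in 6.7.1.1 applies to adherence and, if so, whether person-time stops at the first event.

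The cost is protocol wording and a little more programming. Injection dates and schedules are already needed for 6.3.2.4 and 6.3.2.5, so no new data are required. No clinical rule changes.
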